#### 2.4.3.2. Efficacy

The following secondary efficacy endpoints will assess the effect of the CMCS on clinical parameters of interest, relative to the Control group:

- Change from baseline to 12 months in six-minute walk distance
- Change from baseline to 12 months in left ventricular volumes (end diastolic and end systolic)

### 2.4.4. Safety

The following secondary safety endpoints will be performed on the ITT population and compared between the treatment and control groups:

- Incidence of adverse events (AE) and the corresponding number and percentage of patient
- Incidence of serious adverse events (SAE) and the corresponding number and percentage of patient
- Incidence of device related adverse events (ADE) and the corresponding number and percentage of patient (based on CEC adjudication)
- Incidence of procedure related adverse events and the corresponding number and percentage of patient (based on CEC adjudication)
- Incidence of device related serious adverse events (SADE) and the corresponding number and percentage of patient (based on CEC adjudication)
- Incidence of unanticipated serious adverse device effects (USADE) and the corresponding number and percentage of patient (based on CEC adjudication)
- Incidence of anticipated device effects (AADE) and the corresponding number and percentage of patient (based on CEC adjudication)

- Event Severity
- Incidence of device deficiencies and the corresponding number and percentage of patient

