3.7.2 Study Subject Follow-up Categories

SCREEN-FAILURE → Subject consented but did not meet baseline eligibility criteria (including TEE, if applicable). No study discharge evaluations are necessary.

ENROLLED SCREEN-FAILURE → Subject consented, met all baseline eligibility criteria, but did not meet final angiographic eligibility. Implant was not attempted. Limited study discharge evaluations are necessary, but no follow-up visits are required.

PROCEDURAL SCREEN-FAILURE → Randomized to treatment group, but procedure discontinued before an implant attempt. Full study discharge evaluations are required and the subject is followed through 1-month.

NON-IMPLANTED → Randomized to treatment group, implant attempted, but not successful. Full study discharge evaluations are required and the subject is followed through 12-months.

IMPLANTED → Randomized to treatment group, device successfully implanted. Full study discharge evaluations are required and the subject is followed through 12-months.

CONTROL → Randomized to control group, implant not attempted. Full study discharge evaluations are required and the subject is followed through 12-months.

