5.1.1.6 Adverse Device Effect (ADE)

Adverse event related to the use of an investigational medical device.

Notes:

1. This definition includes adverse events resulting from insufficient or inadequate instructions for use, deployment, implantation, installation, or operation, or any malfunction of the investigational medical device.
2. This definition includes any event resulting from use error or from intentional misuse of the investigational medical device.

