### 2.1.3. Inferential Analysis

Data will be compared between the two groups using bilateral tests at the type I error 5% level.

- *Continuous variables*: the appropriate test will be chosen depending on the data distribution.  
The normality of quantitative data will be tested using the Shapiro-Wilk test.
  - if the normality test pvalue is > 0.05, the data will be considered as normally distributed and the Student test will be used.
  - else, the data will be considered as not normally distributed and the Wilcoxon Rank Sum test will be used.
- *Categorical variables*: the appropriate test will be chosen depending on the expected cell frequencies:
  - If all expected cell frequencies are  $\geq 5$  then the Chi test will be used.
  - Otherwise, the Fisher's exact test will be used.

The 95% confidence interval in regurgitant volume mean difference from baseline to 12 months will be presented by treatment group. If assumptions of normality are violated, the 95% confidence interval will be calculated using the Hodges-Lehmann estimate and distribution-free confidence interval based on a Wilcoxon Rank Sum test.

Further supportive analyses will be conducted which characterize the longitudinal effect of treatment on regurgitant volume in a repeated measures regression model, using a mixed effects model approach. Fixed effects will be treatment group and time effect. Site effect will be a random effect. Interaction between treatment group and site will also be studied.

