## STATISTICAL ANALYSIS PLAN

REDUCE\_FMR - SAP\_V2  
2018\_08\_06\_CT

REDUCE FMR Trial

Page 14/22

- Significance level two-sided 0.05;
- Statistical power to detect design alternative hypothesis is 80%;
- Hypothesized mean regurgitant volume change (baseline to 12-month): Control group = -2.4ml; Treatment group = -12.4ml;
- Hypothesized standard deviation: Control group = 13ml; Treatment group = 13ml;
- 3:1 randomization allocation.

Under the assumptions outlined above, the estimated minimum required sample size is 76 subjects (57 Treatment, 19 Control).

A total of 120 subjects at up to 20 centers will be randomized, allowing for approximately 30% attrition (mortality, missing data and loss to follow-up) in the first 12 months of follow-up.

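### The documents conflict on whether device-related events are tested against Controls, who have no implant attempted; a Treatment-group rate with an exact confidence interval would serve better

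*SAP*

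**What the plan says.** SAP 2.4.4 places nine safety items under a single lead-in: "The following secondary safety endpoints will be performed on the ITT population and compared between the treatment and control groups". Some can occur in either arm (all adverse events, all serious adverse events, procedure-related events). Others are specific to the device. Two examples are "Incidence of device related adverse events (ADE) and the corresponding number and percentage of patient (based on CEC adjudication)" and "Incidence of device related serious adverse events (SADE) and the corresponding number and percentage of patient (based on CEC adjudication)"; the rest are unanticipated serious device effects, anticipated device effects and device deficiencies. No item is exempted from the comparison.

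SAP 2.1.3 says how comparisons are made: "Data will be compared between the two groups using bilateral tests at the type I error 5% level". For categorical data it prescribes chi-square if every expected count is at least 5. "Otherwise, the Fisher's exact test will be used".

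Protocol 5.1.1.6 defines an adverse device effect as "Adverse event related to the use of an investigational medical device". Protocol 3.7.2 describes the Control category as "Randomized to control group, implant not attempted".

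Two places point away from testing. The Type 6 layout in SAP 4.3.1, intended for adverse events, has no P-value column, whereas the other layouts in SAP section 4 have one. Protocol 6.8 says secondary endpoints and observational data will be reported with descriptive statistics.

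**The concern.** A between-arm test is useful when both arms could have the event and the question is whether the device changes its frequency. For the device-specific categories the Control rate is fixed at or near zero by the design. Equal rates would then mean that the device causes essentially no such events, which is not a question worth testing. The p-value mainly reflects how few Controls there are.

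For a permanent implant, the useful figure is how often device-related events occur in those exposed and how high that rate could plausibly be. SAP 2.4.4 gives the count and percentage but no interval. If a p-value is printed in place of an interval, a reader has a number that does not bear on the question and lacks the one that does.

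**Working it through.** **Plan's own figure.** Neither document gives a figure for the safety comparison. The only sized comparison is the primary endpoint (76 evaluable subjects, 57 and 19). A two-sample t-test with difference 10 ml, SD 13 ml and 3:1 allocation gives 81.8% power at 76 and 79.6% at 72, so the stated 76 is reproduced. It has no bearing on safety rates.

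**Inputs.**
- Total: "A total of 120 subjects at up to 20 centers will be randomized" (SAP 2.2). At 3:1 (SAP 1.3.3) this is 90 Treatment and 30 Control.
- Test rule: SAP 2.1.3, two-sided, 5%.
- Control events: 0/30, an assumption based on Protocol 3.7.2 and 5.1.1.6 and varied below.

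**Which test applies.** With x Treatment events and none in Control, the smallest expected count is x × 30/120 = x/4. This is below 5 for every x up to 19, so the SAP's rule selects Fisher's test.

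**Fisher's test.** Given x events in all, the number K falling in Control is hypergeometric, with P(K = 0) = C(90, x)/C(120, x). The two-sided p adds every table no more probable than the observed one.
- x = 11: P(K = 0) = 0.03585. Tables with K ≥ 6 add 0.02760. p = 0.0635.
- x = 12: P(K = 0) = 0.02598. Tables with K ≥ 7 add 0.01008. p = 0.0361.

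| Treatment events | Observed rate | Fisher p v 0/30 |
|---|---|---|
| 5/90 | 5.6% | 0.330 |
| 9/90 | 10.0% | 0.110 |
| 10/90 | 11.1% | 0.065 |
| 11/90 | 12.2% | 0.0635 |
| 12/90 | 13.3% | 0.0361 |

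**Why the ceiling is near 12%.** The exact two-sided 95% upper limit for 0/30 is 1 − 0.025^(1/30) = 11.6%. The test treats the Control rate as unknown up to about that level, although the design makes it close to zero.

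**Chance of p ≤ 0.05.** With no Control event this needs at least 12 Treatment events: P(X ≥ 12) for X binomial(90, rate).
- True rate 5%: 0.2%
- True rate 8%: 5.5%
- True rate 10%: 18.6%
- True rate 12%: 39.5%

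**The informative alternative.** The Clopper-Pearson limits for x/n are the 2.5% quantile of Beta(x, n − x + 1) and the 97.5% quantile of Beta(x + 1, n − x). For 11/90 they are 6.3% and 20.8%.

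**Sensitivity.**
- SAP 2.3.2 removes from ITT the Treatment subjects stopped before an implant attempt; their number is not given. Assuming 76 to 89 Treatment subjects against 0/30, the largest non-significant count is 10 (for 76 to 83) or 11 (for 84 to 89). The ceiling runs from 10/83 = 12.0% to 10/76 = 13.2%.
- With one Control event at 90 v 30, the ceiling is 16/90 = 17.8%; p first falls below 0.05 at 17/90 = 18.9%.

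**The case against.** The strongest reply is that these p-values may never be printed. SAP 2.4.4 says the items are compared but names no test, whereas the SAP's sections on baseline and procedure characteristics name theirs. The Type 6 layout and Protocol 6.8 both suggest description only. This stands as evidence of a conflict. It does not settle the matter: Type 6 is a generic shell shared with medications and deviations, and it does not cancel the lead-in of 2.4.4 or the general rule in 2.1.3.

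A reader might infer that device harm would be presented as a null finding. The documents do not support that. SAP 2.4.4 gives the number and percentage of patients, so the rate is visible. Neither document turns p > 0.05 into a safety conclusion. Major adverse events are analysed separately (SAP 2.4.3.1), and a DSMB and a CEC oversee safety (Protocol 5.1.7 and 5.1.8).

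A reader might also infer that a Control event is impossible. That goes too far. The CEC judges relation to the device as implant, catheter or both (Protocol 5.1.8), every subject has a venogram before randomization (Protocol 3.5.3.3), and adverse events count from consent (Protocol 5.1). Protocol 2.1.2.1 lists contrast injection for venograms among the delivery catheter's uses, but the documents do not say which catheter serves the eligibility venogram. A Control zero is likely but not certain, and one Control event raises the non-significance ceiling.

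**Conclusion.** The point holds as a minor one. SAP 2.4.4 with 2.1.3 calls for a between-arm test of device-specific categories, other parts of the documents point to description only, and the SAP should say which applies. If the test is run, it is uninformative: at 90 v 30 with no Control event it stays non-significant up to an observed 12.2%, where the exact interval reaches 20.8%. These figures assume full enrolment and 0/30 in Control. A smaller Treatment denominator (76 to 89, assumed) moves the ceiling only to about 12% to 13%, and one Control event at 90 v 30 moves it to 17.8%. The 12% is an observed rate, not a true one. The primary analysis is unaffected, and so are the comparisons of all adverse events, all serious adverse events and procedure-related events, because Controls also undergo an index procedure.

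**What to change.** In SAP 2.4.4, separate the device-specific categories (ADE, SADE, USADE, anticipated device effects, device deficiencies) from the rest. Report them for the Treatment group as n/N with exact 95% CIs and no between-group p-value, which agrees with the Type 6 layout and Protocol 6.8. Keep between-group comparisons for all adverse events, all serious adverse events and procedure-related events.

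Use as the main denominator every subject randomized to Treatment in whom the index procedure was started, including those stopped before an implant attempt. Show the implant-attempt subset as a second line. The subset alone is already the SAP's ITT Treatment arm (SAP 2.3.2). It would omit any catheter-related event in subjects stopped early, for example for hemodynamic instability (Protocol 3.7.1.2). Those subjects are followed for safety to 1 month only, so a footnote should state their shorter follow-up.

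List individually any Control event that the CEC judges related to the catheter.

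The cost is a few lines of SAP wording and one extra table row. No new data are needed, and only uninformative p-values are lost.

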### 2.4.5. Observational Data

The following analysis will be performed on the ITT population.

- Long-term safety (through 6 months (+14 days) and 12 months (+30 days) of follow-up):
  - Mortality;
  - Serious adverse events (SAE).
    - NYHA classification at each visit
    - Left ventricular hemodynamics:
      - Left ventricular end diastolic (LVEDD) and systolic (LVESD) dimensions;
      - Ejection fraction (LVEF);
      - Forward cardiac output (CO).
    - Functional Mitral Regurgitation (FMR) echocardiographic assessments
      - Vena Contracta (VC)
      - Effective regurgitant orifice area (EROA)
      - Mitral regurgitation jet area / Left atrial area (MRJA/LAA)
      - Mitral regurgitation grade
        - Left atrial size
        - Mitral annular diameter and area
        - Diuretic dose change from baseline to 6 months of follow-up and to 12 months of follow-up
        - Pulmonary artery systolic pressure (echo derived at rest & during exercise)
        - NT-BNP
        - Kansas City Cardiomyopathy Questionnaire (KCCQ)
        - Quality-of-Life Assessment (SF-12)

### 2.4.6. Supportive Analyses

In addition, a series of supportive, sensitivity analyses will be performed to assess the robustness of the primary analysis results:

- Primary endpoint analysis on ITT population according to etiology of cardiomyopathy (ischemic vs. non-ischemic) through the primary endpoint.
- Primary and secondary efficacy endpoints analysis using LOCF methodology.
- Primary and secondary efficacy endpoints analysis by MR Grade or MR Grade grouping
- Primary and secondary efficacy endpoints analysis using associated baseline characteristics
- Primary endpoint analysis using qualitative measure imputation of core lab derived values where quantification is technically challenging
- Calculation of treatment effect using mitral regurgitation volume and MR grade as parameters in responders and non-responders
- Assessment of treatment effects according to other important clinical subgroups such as:
  - i. Atrial fibrillation vs normal sinus rhythm
  - ii. Baseline MR grade

MEDPASS

INTERNATIONAL

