6.4 Randomization

Randomization will occur in a 3:1 allocation to the Treatment or Control group. Randomization will be stratified according to investigational center in a randomized permuted blocks design.

The study statistician will generate randomization schedules (independent of the Sponsor) and the randomization will be identified either through a web-based portal or by randomization envelopes provided for each center.

^v Left ventricular hemodynamics, FMR assessments and pulmonary artery pressure (echo derived) will also be assessed during exercise in randomized patients at a subset of study sites who have supine bicycle ergometry and echosonographers experienced in imaging acquisition during exercise.

6.5 **Unblinding**

The treatment assignment for a subject will be unblinded only in the following circumstances:

- 1) In the event of medical emergency where it is medically necessary to know if the subject received an implant.
- 2) After a randomized study subject has completed their 12-month visit, the treatment assignment for that subject can be unblinded.

The DSMB and/or CEC, upon request, may be provided with the randomization assignment of a particular subject(s) or to assess safety trends between study groups. This can be provided by the study statistician and does not require unblinding of critical site and study personnel.

6.6 **Primary Endpoint Evaluation & Sample Size Assumptions**

The primary endpoint of the study is to demonstrate a significantly greater improvement from baseline in Regurgitant Volume (assessed by echo corelab) associated with the CARILLON Mitral Contour System at 12-months, relative to the Control group.

Parameter of Interest

The parameter of interest for each treatment group is the mean change from baseline in regurgitant volume, in milliliters, at 12-months.

Hypotheses

$$H_0: \mu_{\text{CARILLON}} = \mu_{\text{CTL}}$$

$$H_a: \mu_{\text{CARILLON}} \neq \mu_{\text{CTL}}$$

where μ_{CARILLON} is the mean change in regurgitant volume for those randomized to the Treatment group, and μ_{CTL} is the mean change in regurgitant volume for those randomized to the Control group.

Sample Size Estimation

Sample size is calculated using a comparison of means (Student's t test). The minimum required sample size was calculated under the following assumptions:

- Significance level two-sided 0.05
- Statistical power to detect design alternative hypothesis is 80%

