- Hypothesized mean regurgitant volume change (baseline to 12-month) in the Control group = -2.4 ml
- Hypothesized mean regurgitant volume change (baseline to 12-month) in the Treatment group = -12.4 ml
- Hypothesized standard deviation:

- Treatment group = 13 ml,
- Control group = 13 ml
- 3:1 randomization allocation

Under the assumptions outlined above, the estimated minimum required sample size is 76 subjects (57 Treatment, 19 Control).

Justification for Sample Size Assumptions

Assumptions for sample size calculations are derived from a two previous studies of subjects implanted with the CARILLON Mitral Contour System in a similar patient population – the TITAN and TITAN II studies. The hypothesized mean change (baseline to 12 months) for the Control group is conservatively assumed to be approximately -2.4 ml. The hypothesized mean change for the Treatment group, and the standard deviations for both groups, is expected to be similar to that observed in the TITAN and TITAN II study cohorts 12 months after implantation. In these studies, the observed change in regurgitant volume at 12 months was -14.1 ml. The observed mean difference between the populations is adjusted to account for as many as 15% of the Treatment group subjects not receiving a permanent implant (Non-Implanted Treatment group patients) but still counted in the intent to treat analysis, thus yielding regurgitant volume results similar to the Control group, without compromising the power of the study. This study assumes a -10 ml mean difference in regurgitant volume between the study populations.

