## 2. STATISTICAL METHODS

### 2.1. General Statistical Considerations

#### 2.1.1. Handling Missing Data

If any subject does not have endpoint data available (12-month data), the primary analysis will assume that data as missing and that subject's data will not be included in the primary analysis.

Missing data will be imputed for all missing primary, secondary and observational endpoint parameters using a last observation carried forward (LOCF) methodology and will be presented as a sensitivity analysis to assess the robustness of results.

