### 2.4.2. **Primary Endpoint**

The primary analysis will be performed on the Intent to treat (ITT) population.

The primary efficacy endpoint is to compare the change in regurgitant volume from baseline at 12 months between the treatment and control groups using a two-sided, two-sample t-test (or Wilcoxon Rank sum test as appropriate). The corresponding 95% confidence interval on the between-group difference will also be calculated and presented.

A sensitivity analysis of the primary efficacy endpoint analysis on the ITT population will be performed, using the last observation carried forward (LOCF) missing data imputation on the regurgitant volume at 12 months. The same comparison analysis as mentioned above for the primary efficacy endpoint will be performed.

Two other additional analyses will be performed on the primary efficacy endpoint on:

- As-treated population
- Per-protocol population

The same comparison analysis as for the primary efficacy endpoint mentioned above will be used

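### The plan sets no regurgitant-volume score for a readable 12-month echo with MR too small to quantify, so the primary exclusion rule could select on outcome

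*SAP*

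**What the plan says.** Protocol 6.6 and SAP 2.2 define the parameter of interest as the mean change from baseline in regurgitant volume, in millilitres, at 12 months, as assessed by the echo core lab. SAP 2.4.2 compares the arms by t-test, or by Wilcoxon test if normality is rejected.

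For a subject without 12-month endpoint data, SAP 2.1.1 states that "the primary analysis will assume that data as missing and that subject's data will not be included in the primary analysis". Protocol 6.2 has the same rule. The sensitivity analysis in SAP 2.4.2 repeats the comparison "using the last observation carried forward (LOCF) missing data imputation on the regurgitant volume at 12 months".

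SAP 2.4.6 lists among the supportive analyses: "Primary endpoint analysis using qualitative measure imputation of core lab derived values where quantification is technically challenging". It gives no trigger, no conversion from grade to millilitres and no imputed values. The text of the Echocardiogram Protocol (Protocol Appendix E) is not reproduced in the available document.

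**The concern.** An echo can lack a regurgitant volume for two quite different reasons. The image may be too poor to read, in which case the result is unknown. Or the image may be readable and show no jet, or one too small to measure, in which case the result is known and favourable. The SAP covers both with one phrase and gives neither a value in the primary analysis.

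For the second kind, exclusion depends on the 12-month outcome. If the device works as the design assumes, very small residual volumes are commoner in Treatment, so the excluded subjects come mostly from that arm and have larger reductions than its average. A blinded core-lab reading would be discarded and the estimated difference would move toward no effect.

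LOCF would replace such a reading with an earlier, probably larger, volume. The plan does not say whether baseline counts as an earlier observation. If it does, and the 1- and 6-month echoes were also too small to quantify, a subject with almost no residual regurgitation would be scored as unchanged.

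**Working it through.** **1. The plan's own figure.** Inputs from Protocol 6.6: "Significance level two-sided 0.05"; assumed mean changes of −2.4 ml (Control) and −12.4 ml (Treatment); SD 13 ml in each arm; 3:1 allocation. The difference is 12.4 − 2.4 = 10 ml. For a two-sample t-test the noncentrality is 10 / (13 × √(1/n_T + 1/n_C)).
- 54/18: 10 / (13 × 0.272) = 2.83, power 79.6%.
- 57/19: 10 / (13 × 0.265) = 2.90, power 81.8%.

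So 76 (57/19) is the smallest 3:1 total that reaches 80%, as stated.

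**2. Evaluable number.** Protocol 6.7 randomizes 120 and allows about 30% attrition, with missing data included: 120 × 0.70 = 84, or 63/21. The noncentrality is 10 / (13 × 0.252) = 3.05 and power is 85.5%. This is the starting point below.

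**3. Assumptions that the documents do not supply.**
- Baseline mean: the earlier change of −14.1 ml (Protocol 6.6) divided by the largest reported reduction of 46% (Protocol 1.3.6.2) gives 14.1 / 0.46 = 30.7 ml. This is rough, because the 46% is from TITAN and the 14.1 ml is from TITAN and TITAN II. Values of 30, 35 and 40 ml are used.
- Baseline SD 13 ml, and correlation of baseline with change −0.5. The 12-month SD is then √(169 + 169 − 169) = 13 ml.
- Every 12-month volume below a limit L of 5 or 10 ml cannot be quantified. Volumes are floored at 0.

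Hand check at baseline 30 and L = 5. The Treatment mean at 12 months is 30 − 12.4 = 17.6 ml, and Φ((5 − 17.6)/13) = Φ(−0.97), about 17%. The Control mean is 27.6 ml, and Φ((5 − 27.6)/13) = Φ(−1.74), about 4%.

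**4. Simulation, 63/21 before exclusion (differences in ml in favour of Treatment).**

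| Baseline | L | Excluded, Treatment / Control | Difference, all kept → excluded | Power, all kept → excluded |
|---|---|---|---|---|
| 30 | 5 | 16.5% / 4.2% | 9.57 → 8.69 | 84% → 75% |
| 30 | 10 | 27.9% / 8.8% | 9.55 → 8.09 | 84% → 66% |
| 35 | 5 | 8.8% / 1.7% | 9.82 → 9.14 | 85% → 79% |
| 35 | 10 | 16.6% / 4.1% | 9.83 → 8.68 | 85% → 75% |
| 40 | 5 | 4.2% / 0.6% | 10.01 → 9.59 | 86% → 83% |
| 40 | 10 | 8.8% / 1.7% | 9.96 → 9.16 | 86% → 80% |

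The loss runs from 10.01 − 9.59 = 0.42 ml to 9.55 − 8.09 = 1.46 ml. In the first row, 63 × 0.165 = 10.4 Treatment and 21 × 0.042 = 0.9 Control subjects are excluded, so 92% of them are Treatment, against 75% from the allocation alone. Excluded Treatment subjects average −18 to −24 ml, against about −12.4 ml for the arm.

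A separate run at baseline 31 ml agrees: 9.6 → 8.7 ml and 83% → 75% at L = 5, and 8.1 ml and 67% at L = 10.

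**5. The remedy.** At baseline 31 ml, scoring the affected echoes at L/2 restores power to 82–83%, with 5% rejection under the null. Scoring them at 0 ml gives 84–86% power over the grid in step 4. It overshoots slightly at L = 10, with a difference of 10.2–10.3 ml against 9.6–10.0 ml with all true volumes kept.

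**6. The other cause.** If images fail at random in both arms, 10% or 20% missing leaves the difference at 10 ml and power at 82% or 77%. Numbers are lost, but there is no bias.

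**The case against.** The strongest reply is that SAP 2.4.6 speaks only of technical difficulty. It mentions neither small jets nor the 12-month visit nor an arm, and poor windows or awkward jets fit it equally well. A reader might infer that the plan drops the best responders, mostly from Treatment, and so shrinks the effect. The documents do not support that as fact. The rule would remove low residual volumes, which include subjects with low baseline volumes (entry allows 2+ regurgitation) and some Controls. This objection stands.

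Appendix E may already hold a scoring rule, and that the core lab would leave such an echo blank is an inference. This also stands, and it makes a check necessary. Still, if these echoes already had a volume in the primary analysis, the supportive imputation would have little purpose.

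The size is also open to challenge. Prior studies reported partial reductions (32–46% at 12 months in TITAN), so near-zero residual volume may be uncommon. The normal model puts about 9% of Treatment at or below 0 ml when baseline is 30 ml. A gamma model with the same mean and SD, at a 5 ml limit, excludes 10.7% versus 0.3% and loses about 0.6 ml. A reader might also start from 57/19 and reach power of 62–70%, but that ignores the attrition allowance, which already includes missing data and leaves 63/21.

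Finally, the bias is conservative for a superiority claim, and deaths or withdrawals could bias the complete-case result the other way. Both points are fair, so the net direction over all missing data is not settled. Neither is a reason to treat an observed result as missing.

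**Conclusion.** The gap holds in conditional form. The primary analysis requires a number, the only provision for hard-to-quantify values is a supportive analysis with no stated values, and the available text does not distinguish too small from unreadable. To the extent that small residual regurgitation is the reason, the exclusion selects on outcome, weighs mainly on Treatment under the design assumptions, and biases the difference toward no effect. LOCF does not correct it.

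On the assumptions in steps 2 and 3, the shrinkage is about 0.4–1.5 ml of a planned 10 ml, and power falls from about 83–86% to about 66–83%. Baseline volume, its spread and the quantification limit are all assumed, so these figures show what could happen and do not predict it. The documents do not show how often such echoes will occur. The change is worth making because the rule costs little and matters little if such echoes prove rare.

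**What to change.** First check the Echocardiogram Protocol (Appendix E) for an existing scoring rule. If there is one, cite it in the SAP. If not, amend SAP 2.4.2 before unblinding:

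- The blinded core lab records a reason for each echo without a regurgitant volume: none/trace or too small to quantify, or unreadable.
- Echoes in the first category receive one pre-set value, half the core lab's stated limit, and stay in the primary ITT analysis. LOCF is not applied to them. A score of 0 ml is reported as a sensitivity value.
- Only unreadable echoes count as missing.
- Counts by reason and arm are reported.
- The analysis that excludes the scored echoes is kept as a sensitivity analysis.

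The cost is a paragraph of SAP text and one reason code in the core-lab file. The drawback is that a fixed score for some subjects makes the change data less normal, so the Shapiro-Wilk rule in SAP 2.1.3 is more likely to switch the primary test from the t-test to the Wilcoxon test.

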6.9 Supportive Analyses & Missing Data Imputation

The following supportive analyses will also be undertaken.

- Assessment of treatment efficacy in subjects receiving a permanent implant through the primary endpoint – “as-treated” analysis
- Assessment of treatment efficacy in subjects receiving a permanent implant and who did not receive alternative or confounding therapies (e.g., CRT therapy, transplant, stenting, etc.) through the primary endpoint – “per protocol” analysis
- Assessment of treatment efficacy according to etiology of cardiomyopathy (ischemic vs. non-ischemic) through the primary endpoint
- Assessment of treatment efficacy according to baseline LV ejection fraction ($\leq 40\%$ vs. 41-50%) through the primary endpoint

Missing data will be imputed using a last observation carried forward (LOCF) methodology and be reported separately for:

- the primary and secondary endpoint parameters
- the observational parameters
- the primary (intent to treat) and supportive analyses noted above.

7 **Ethical, Regulatory, and Administrative Considerations**

This study will be conducted in accordance with the International Standard ISO 14155:2011, recommendations guiding physicians in biomedical research involving human subjects adopted by the 18th World Medical Assembly, Helsinki, Finland, 1964 and later revisions, Good Clinical Practice: Consolidated Guidance (ICH E-6) and any regional or national regulations, as appropriate.

Only centers willing and able to comply with these practices will be included in the study.

7.1 **Informed Consent**

To protect the rights and welfare of subjects, this clinical study will be conducted in conformance to the International Standard ISO 14155: 2011, Section 4.7: Informed Consent.

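### SAP 2.4.6 lists eight subgroup factors in an open list with no interaction test; if the default 5% two-group test is run within each stratum, a uniform effect would look discordant in about half of the factors

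*SAP*

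**What the plan says.** SAP 2.4.6 (Supportive Analyses) repeats the primary endpoint analysis by etiology of cardiomyopathy and the efficacy analyses by MR grade or some grouping of it. It then adds "Assessment of treatment effects according to other important clinical subgroups such as": rhythm, MR grade again, LVEDD around 65 mm, ejection fraction at 40%, left atrial dimension, mitral annular diameter and gender. That makes eight distinct factors. Left atrial dimension and annular diameter have no cut-point, and the MR-grade grouping is undecided.

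The section names no test. SAP 2.1.3 gives the general rule: "Data will be compared between the two groups using bilateral tests at the type I error 5% level". SAP 2.4.2 (Primary Endpoint) defines the primary analysis as a two-sample t-test, or a rank-sum test where appropriate. The only interaction in the SAP is treatment by site, in the supportive repeated-measures model of 2.1.3. No multiplicity or interpretation rule is given for subgroups.

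Protocol 6.9 plans only two subgroup factors: "Assessment of treatment efficacy according to etiology of cardiomyopathy (ischemic vs. non-ischemic) through the primary endpoint", and baseline ejection fraction. The other six come from the SAP.

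**The concern.** Whether the device effect differs between strata is a question about the difference between two treatment effects. Testing each stratum against zero does not answer it. When the true effect is the same everywhere, one stratum can reach p<0.05 and the other miss it simply because each is small. With 3:1 allocation and about 21 evaluable Controls, an even split leaves about 10 Controls per stratum, and a minority stratum has fewer.

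SAP 2.4.6 presents these analyses as a check on the robustness of the primary result. A method that often shows a contrast between strata under a uniform effect is a poor check. The open list, the undecided grouping and the missing cut-points add choices that could be made after the data are seen.

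**Working it through.** **Inputs from SAP 2.2.** "Significance level two-sided 0.05"; mean changes "Control group = -2.4ml; Treatment group = -12.4ml", a difference of 10 ml; standard deviations "Control group = 13ml; Treatment group = 13ml"; "3:1 randomization allocation"; 120 randomized with about 30% attrition, so 120 × 0.70 = 84 evaluable (63 Treatment, 21 Control).

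**Assumptions not in the documents.** Two levels per factor, splits of 50/50 or 70/30, 3:1 kept within each stratum, and a t-test in each stratum.

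**Reproducing the plan's figure.** Power comes from the noncentral t distribution with noncentrality 10 / (13 × √(1/n_T + 1/n_C)). For 54 + 18 = 72 subjects power is 79.6%; for 57 + 19 = 76 it is 81.7%. So 76 is the smallest exact 3:1 total reaching 80%, as the SAP states.

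**Discordance with a uniform 10 ml effect.** For two disjoint strata with powers p and q, the chance that exactly one is significant is p(1 − q) + q(1 − p).

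| Split | Stratum sizes (T/C) | Power | Exactly one significant |
|---|---|---|---|
| 50/50 | 32/11 and 31/10 | 57.5%, 54.1% | 0.575 × 0.459 + 0.541 × 0.425 = 49% |
| 70/30 | 44/15 and 19/6 | 71.5%, 35.0% | 0.715 × 0.650 + 0.350 × 0.285 = 56% |

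**Sensitivity.**
- With 76 evaluable, the results are 50% (50/50) and 56% (70/30).
- With 84 evaluable and more uneven splits, discordance is 64% at 80/20 and 73% at 90/10.
- If all 120 were evaluable, the 50/50 figure is 41%.
- With a true effect of 5 ml and 84 evaluable, it is 30% (50/50) to 31% (70/30).
- With no effect, it is 2 × 0.05 × 0.95 = 9.5%.

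**Across eight factors.** All factors re-cut the same patients, so these figures come from simulation with 84 subjects and eight independently assigned two-level factors. With a uniform 10 ml effect and 50/50 splits, about 4 of the 8 are discordant on average, and the chance of at least one is about 90%. With no effect, at least one within-stratum p<0.05 occurs in about 37% of trials.

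**Under interaction tests.** The false rate is about 5% per factor whatever the common effect (simulated 4–6%). Across eight factors the chance of at least one is 1 − 0.95⁸ = 34% if the tests are independent, and about 32% simulated.

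**The case against.** The strongest reply is that the SAP never says the subgroups will be tested stratum by stratum. Section 2.4.6 speaks only of analysis by, or according to, a factor, which an interaction model would also satisfy. This stands as a limit on the claim: a reader might infer that the plan chose within-stratum tests over interaction tests, and the documents do not say so for every factor. But the section applies the primary endpoint analysis to subgroups, that analysis is defined as a two-group test, and the general rule is also a two-group test. Nothing in the text displaces that default.

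A reader might also compute 1 − 0.95¹⁶ = 56% as the chance of at least one false positive with no effect. That requires 16 independent tests, which cannot hold when every factor reuses the same patients; about 37% is the better figure. Sixteen is not a count from the documents either: MR grade could have three levels, and two factors have no stated levels.

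Two further points stand. The analyses are labelled supportive, no subgroup conclusion is planned, and the primary type I error is untouched. And with no effect the proposed method gains little (about 32% against 37%). Its real gain is in avoiding false heterogeneity when the device works.

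**Conclusion.** The point holds as a conditional, low-severity one. The plan lists eight subgroup factors in an open list, with no interaction term, no rule of interpretation and some groupings unfixed. If its default tests are run within strata, a uniform 10 ml effect would appear in one stratum and not the other for about 49% to 56% of factors. That rests on 84 evaluable subjects, SD 13 ml, two levels per factor and splits between 50/50 and 70/30. It is not a general coin toss per factor: the rate is about 30% at a true effect of 5 ml and 9.5% with none, and it rises above 60% for splits of 80/20 or more uneven. The risk is misreading of supportive results; the primary comparison is unaffected.

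**What to change.** In SAP 2.4.6, for each listed factor, fit one intention-to-treat model of 12-month change in regurgitant volume with treatment, factor and treatment-by-factor interaction. Report the interaction estimate with its 95% confidence interval and p-value, plus stratum estimates with confidence intervals. State that within-stratum p-values will not be interpreted.

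Close the list. Before unblinding, fix the MR-grade grouping and the cut-points for left atrial dimension and annular diameter, or model those two as continuous. Label the results exploratory, and say that across eight factors about a 32% chance of at least one false-positive interaction remains.

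The cost is SAP wording and giving up within-subgroup p-values. No extra subjects or data are needed, and the primary analysis does not change.
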